**Observational Cohort Study of a National Extracorporeal Membrane Oxygenation Service for Adults
With Respiratory Failure: the NHS ECMO Study**

NCT: NCT03979222

Statistical Analysis Plan

Authors: [name], [name], [name], [name]
Approved by NHS ECMO steering group.

SAP version: 25/02/2019

The aims of the project are:

- To describe the cohort of patients supported by the NHS England-commissioned Respiratory ECMO service from inception (Dec 2011) to now;
- To report the outcomes (morbidity and mortality) of patients supported by the NHS England-commissioned Respiratory ECMO service from inception (Dec 2011) to June 2018;
- To identify factors predictive of duration of stay, complications (to be specified) and survival.

To achieve this, we intend to perform a longitudinal observational cohort study of this patient group.

1. Identification of cohort

The national severe acute respiratory failure was commissioned in 2011 to provide extracorporeal membrane oxygenation (ECMO) for adult patients with severe acute respiratory failure. ECMO can be delivered in both VV (venovenous - supporting lungs only) and VA (venoarterial - supporting heart and lungs) modalities.

The eligibility criteria for this service is outlined in a commissioning document published in 2011.

Patients have been identified which meet the following inclusion criteria, as per the 2011 commissioning document:

- Admitted under the national commissioned service
- Age ≥ 16 years
- Admitted between 1st December 2011 and 31st December 2017.

For patients who have multiple runs during the same hospital admission, only the first run will be included in analysis. Those who have configuration changes during the same ECMO run will be counted as a single run for the purposes of analysis.

Patient data is contained in two databases – the Extracorporeal Life Support Organisation (ELSO) database, containing data from the ELSO runsheets of each patient having received ECMO, and the ‘tracker’ database kept by Public Health England to monitor the commissioned service.

The tracker identifies 1,317 patients who meet the above criteria, but only has basic data for these (date, centre and outcome). All patients with corresponding ELSO records will be entered into formal analysis.

2. Data checks

Data checks will follow the recommendations from Kirkwood and Sterne [1]. Outliers in continuous variables will be detected using ranges and plotting distributions within each treatment. Categorical variables will be tabulated and unexpected distributions further checked. Consistency checks between two or more variables will also be performed, e.g. plotting weight against age.

3. Descriptive statistics

The broad guidelines of descriptive statistics are as follows: (1) continuous data will be summarised with means and standard deviations if normally distributed, or with median and inter-quartile range if asymmetric or otherwise non-normal; (2) categorical data will be summarised by counts and percentage per level within factors; (3) missing count and proportion will also be reported. A table will be prepared with descriptive variables between survivors and non-survivors; 95% confidence intervals will be given.

The full list and data type of variables can be found in the appendix. Those which have been identified as having large numbers of missing data, unlikely to be suitable for inclusion in analysis, have been highlighted in yellow. A summary will be provided for these variables.

All statistical analysis and methodology will be reported according to the Strengthening the Reporting of Observational Studies in Epidemiology (STROBE) statement [2].

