3.3. Features of ECMO treatment itself

- Which ECMO centre (can use numbers to anonymise)
- Initial ECMO modality (e.g. VV, VA, VV-CO₂R, other)
- Transport on ECMO (%)
- Duration of ECMO therapy

- Repeat ECMO (several runs in same patient)
- Change of configuration during ECMO

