3.4. Patient outcome data

The primary outcome of interest is the % of patients discharged alive from the ECMO ICU.

Secondary outcomes include:

- duration of ECMO therapy
- duration of mechanical ventilation
- ICU length of stay
- discharge destination

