3.5. Complications

- Mechanical
 - Oxygenator failure
 - Pump failure
 - Raceway rupture
 - Other tubing rupture
 - Cannula problems
 - Circuit change
 - Heat exchanger malfunction
 - Thrombosis/clot
 - Clot haemofilter
 - Air in circuit
- Haemorrhage
 - GI haemorrhage
 - Peripheral cannula site bleeding
 - Mediastinal cannulation site bleeding
 - Surgical site bleeding
- Neurological
 - Brain death
 - Seizures
 - Clinically determined
 - EEG confirmed
 - Cerebral diffuse ischaemia
 - Cerebral infarction
 - Intracerebral haemorrhage
 - Neurosurgical intervention
- Renal
 - Renal replacement therapy required
- Cardiovascular
 - Cardiac arrest requiring CPR
 - Arrhythmia
 - Cardiac tamponade
 - Haemorrhagic tamponade
- Pulmonary
 - Pneumothorax
 - Pulmonary Haemorrhage
- Metabolic
 - Hyperbilirubinaemia
 - Moderate haemolysis
 - Severe haemolysis
- Limb-related
 - Fasciotomy
 - Amputation
 - Limb ischaemia requiring reperfusion cannula
- Infectious (culture proven)

Complication data will be summarised for the entire cohort, rather than entered into regression analysis.

4. Regression analysis

It would be useful to perform a regression analysis on the variables listed in 3.1 to 3.3 above, in order to identify factors independently associated with the primary outcome (mortality) and the secondary outcome (length of stay, complication).

The general modelling building strategies are: (1) clinical knowledge will decide which variables are important as potential predictors of outcomes and which should be accounted for in the models as potential confounders and/or effect modifiers (interactions); (2) in addition to clinical knowledge, univariate associations will be investigated between the primary outcome and exposure predictors. This will show which predictors are *a priori* associated with outcomes, and how those effects change when accounting for confounders and/or interactions; (3) in a multiple regression context, collinearity or high correlations between predictors can lead to unstable regression coefficients and extremely large standard errors. One way of avoiding collinearity is to select among a group of highly correlated predictors, the predictor most strongly associated with the response.

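### The first-run rule is applied to outcomes as well as predictors, so ECMO days and complications on later runs of an admission drop out of the patient-level morbidity figures

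*SAP*

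**What the plan says.** The second aim, at the start of the SAP, is "To report the outcomes (morbidity and mortality) of patients supported by the NHS England-commissioned Respiratory ECMO service". Section 1 then sets the unit of analysis: "For patients who have multiple runs during the same hospital admission, only the first run will be included in analysis". A change of circuit configuration does not start a new run: "Those who have configuration changes during the same ECMO run will be counted as a single run for the purposes of analysis". The detailed data come from ELSO runsheets. The tracker database holds only date, centre and outcome for its 1,317 patients.

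Repeat-run patients are not excluded. Section 3.3 lists "Repeat ECMO (several runs in same patient)" among the treatment features to describe, and the appendix carries it as an integer variable.

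The primary outcome in section 3.4 is a patient status: "The primary outcome of interest is the % of patients discharged alive from the ECMO ICU". The secondary outcomes there include "duration of ECMO therapy" and "ICU length of stay". On complications, section 3.5 says: "Complication data will be summarised for the entire cohort, rather than entered into regression analysis". The appendix adds undefined variables for weaning from ECMO and for death on ECMO. The SAP nowhere says which outcomes are measured on the first run and which over the whole admission.

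**The concern.** Restricting to the first run is sensible for pre-ECMO predictors: it gives one record per patient and a clear time zero. It does not suit outcomes that are meant to describe what happened to the patient. Someone who comes off a first run, is cannulated again and has an intracerebral haemorrhage on the second run contributes, on a literal reading, only the first run's days and no haemorrhage.

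The rule also mixes units within one set of results. Survival and ICU stay cover the whole stay, while ECMO duration and complications stop at the end of the first run. This carries into the comparison of survivors with non-survivors (section 3). It also reaches the mortality model in section 4, whose candidate variables include ECMO duration from section 3.3: first-run duration would be related to a status that a later run may have decided.

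**Working it through.** **Which outcomes the rule can reach**

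- *Alive at ECMO ICU discharge (primary, 3.4).* Defined at ICU discharge, not at the end of a run. A patient who dies on a second run before leaving the ECMO ICU is not discharged alive. Change caused by the rule: none.
- *ICU stay, duration of ventilation, discharge destination (3.4).* Listed without reference to a run; not affected as written.
- *ECMO duration (3.4) and complications (3.5).* These can belong to a run, and the source is the runsheet. Under the literal rule, later-run content is dropped. The tracker cannot restore it.
- *Weaned off and died on ECMO (appendix).* Undefined. If coded from run 1, a patient who dies on run 2 is recorded as weaned and not as a death on ECMO, yet is a death for the primary outcome.

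**Direction.** Adding a later run can add ECMO days or a first occurrence of a complication, and cannot remove either. Patient totals and ever-occurred rates based on the first run are therefore equal to or below the all-run values.

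**Size.** The SAP states no figure that can be reproduced here and no repeat-run rate, so the size is bounded by assumption.

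- N = 1,317, the tracker count in section 1. This is an upper limit, because only patients with ELSO records are analysed.
- r = share of patients with a second run, assumed 1% to 10%, with at most two runs each.
- p = risk of a given complication per run, assumed 5% to 40%, equal and independent across runs.

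Any-run rate = p + r(1 − p)p, so understatement = r(1 − p)p. For r = 10% and p = 40%: 0.10 × 0.60 × 0.40 = 0.024, or 2.4 points.

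Share of ECMO days lost, if the second run is as long as the first, = r/(1 + r). For r = 10%: 0.10/1.10 = 9.1%.

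For scale, the 95% half-width = 1.96 × √(p(1 − p)/1,317).

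| r | Patients (N × r) | Understatement, p = 5% | p = 20% | p = 40% | ECMO days lost |
|---|---|---|---|---|---|
| 1% | 13 | 0.05 points | 0.16 | 0.24 | 1.0% |
| 3% | 40 | 0.14 | 0.48 | 0.72 | 2.9% |
| 5% | 66 | 0.24 | 0.80 | 1.20 | 4.8% |
| 10% | 132 | 0.48 | 1.60 | 2.40 | 9.1% |
| 95% half-width | – | 1.18 | 2.16 | 2.65 | – |

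In every cell the understatement is smaller than the half-width. If the risk on the second run is q rather than p, the understatement is r(1 − p)q, so it scales in proportion to q.

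**The case against.** The strongest defence is that one run per patient is an openly stated design choice. It avoids counting a patient twice, keeps records independent and matches outcomes to the pre-ECMO state. Repeat ECMO is reported in its own right, so nothing is hidden. The second aim speaks of outcomes of patients but does not promise complications accumulated over every run. The likely loss is within sampling error, and a median duration (section 3 uses medians for skewed data) may hardly move when a few per cent of patients gain days.

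Much of this stands. The rule is not an error for predictors, the effect is probably modest, and a median would be less sensitive than the share of days in the table. Two parts do not stand. A count of repeat runs does not tell the reader what happened during them. And a bias that can go in only one direction is not covered by a confidence interval, which describes sampling error around the understated value.

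A reader might also infer more than the SAP supports:

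- *That deaths on later runs disappear from mortality.* They do not, because the primary outcome is status at ECMO ICU discharge.
- *That such patients will be recorded as weaned.* This is conditional: the two variables are undefined appendix rows, and nothing says they are coded from run 1.
- *That a patient moved between ECMO centres is counted twice, once as a survivor.* The SAP describes no such transfers and no second record, and the appendix lists a patient identifier.
- *That a particular share of deaths on ECMO is miscoded.* This would need a repeat-run rate, a death rate on later runs and an overall rate of death on ECMO, none of which the SAP gives.

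**Conclusion.** The point holds for ECMO duration and complications, and conditionally for the two appendix variables. It does not hold for the primary outcome or for ICU stay. Read literally, section 1 makes the patient-level morbidity of the second aim equal to or lower than the truth, and the SAP neither says so nor labels the affected figures.

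The direction is certain and the true size is unknown. The ranges of about 0.05 to 2.4 percentage points for a complication rate and about 1% to 9% of ECMO days rest wholly on the assumed repeat rate, the assumed equal and independent risk per run, and later runs as long as the first. A higher risk on later runs would enlarge the loss. A smaller analysed cohort would leave these percentages unchanged and widen the half-widths. This is a modest but systematic bias that is cheap to remove.

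**What to change.** In section 1, keep one record per patient and take all pre-ECMO predictors from the first run. Then state the outcome unit in sections 3.4 and 3.5:

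- ECMO duration is the sum of days over all runs of the admission.
- A complication counts if it occurs in any run of the admission.
- Weaned off ECMO and died on ECMO are taken from the last run.
- First-run-only duration and complication figures, and the number of patients with repeat runs, are shown alongside.

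Say explicitly that the primary outcome, ICU stay, ventilation duration and discharge destination refer to the stay and not to a run.

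The cost is SAP wording and a linkage of runs by the patient identifier already in the appendix. The downside is a little more data management and slightly less favourable complication, duration and weaning figures.

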3.1. Basic descriptive statistics on the patient cohort

- Number of patients
 - Both in total and per centre
- Number per calendar year (2012-2017, as full data allow)
 - Both in total and per centre
- Age
- Sex
- Weight

3.2. Clinical features of patients pre-ECMO

- Primary diagnosis
- Diagnostic category (bacterial pneumonia, viral pneumonia, aspiration pneumonitis, asthma, trauma, burns, other acute respiratory diagnosis, other non-respiratory diagnosis, unspecified)
- Pre-ECMO cardiac arrest (%)
- Time from admission to intubation
- Time from intubation to ECMO initiation
- Biochemical variables
 - pH
 - PaO₂
 - PaCO₂
 - FiO₂
 - PaO₂/FiO₂ ratio
 - SaO
- Ventilator settings
 - Ventilation mode
 - PEEP
 - Ventilator rat

3.3. Features of ECMO treatment itself

- Which ECMO centre (can use numbers to anonymise)
- Initial ECMO modality (e.g. VV, VA, VV-CO₂R, other)
- Transport on ECMO (%)
- Duration of ECMO therapy

- Repeat ECMO (several runs in same patient)
- Change of configuration during ECMO

3.4. Patient outcome data

The primary outcome of interest is the % of patients discharged alive from the ECMO ICU.

Secondary outcomes include:

- duration of ECMO therapy
- duration of mechanical ventilation
- ICU length of stay
- discharge destination

3.5. Complications

- Mechanical
 - Oxygenator failure
 - Pump failure
 - Raceway rupture
 - Other tubing rupture
 - Cannula problems
 - Circuit change
 - Heat exchanger malfunction
 - Thrombosis/clot
 - Clot haemofilter
 - Air in circuit
- Haemorrhage
 - GI haemorrhage
 - Peripheral cannula site bleeding
 - Mediastinal cannulation site bleeding
 - Surgical site bleeding
- Neurological
 - Brain death
 - Seizures
 - Clinically determined
 - EEG confirmed
 - Cerebral diffuse ischaemia
 - Cerebral infarction
 - Intracerebral haemorrhage
 - Neurosurgical intervention
- Renal
 - Renal replacement therapy required
- Cardiovascular
 - Cardiac arrest requiring CPR
 - Arrhythmia
 - Cardiac tamponade
 - Haemorrhagic tamponade
- Pulmonary
 - Pneumothorax
 - Pulmonary Haemorrhage
- Metabolic
 - Hyperbilirubinaemia
 - Moderate haemolysis
 - Severe haemolysis
- Limb-related
 - Fasciotomy
 - Amputation
 - Limb ischaemia requiring reperfusion cannula
- Infectious (culture proven)

Complication data will be summarised for the entire cohort, rather than entered into regression analysis.

4. Regression analysis

It would be useful to perform a regression analysis on the variables listed in 3.1 to 3.3 above, in order to identify factors independently associated with the primary outcome (mortality) and the secondary outcome (length of stay, complication).

The general modelling building strategies are: (1) clinical knowledge will decide which variables are important as potential predictors of outcomes and which should be accounted for in the models as potential confounders and/or effect modifiers (interactions); (2) in addition to clinical knowledge, univariate associations will be investigated between the primary outcome and exposure predictors. This will show which predictors are *a priori* associated with outcomes, and how those effects change when accounting for confounders and/or interactions; (3) in a multiple regression context, collinearity or high correlations between predictors can lead to unstable regression coefficients and extremely large standard errors. One way of avoiding collinearity is to select among a group of highly correlated predictors, the predictor most strongly associated with the response.

In addition, during modelling development (in a multiple regression context) suitable transformations (such as log, box-cox transformation) will be used if there is evidence of poor fit or influential measurements. Model selection will be achieved via likelihood ratio tests (LRT) and declaring statistical differences at p-values < 0.05. Non-nested models will be compared using Akaike's information criterion (AIC), where a decrease in ≥ 10 units will indicate important statistical differences between models ([3]).

The specific regression analysis depends on the type of outcome variables. If the outcome is mortality or complication, logistic regression analysis will be performed; if the outcome is length of stay, Poisson regression or negative binomial regression will be used.

Predefined subgroup analysis will be undertaken on the following variables of clinical interest: age, diagnostic category, BMI, calendar year of ECMO run i.e. trend in outcome over time, and centre. It is important to stress that the centre comparative analysis is used here as a proxy for the underlying population, and may not be included in any data for publication.

5. Missing data analysis

All essential variables are expected to be complete or at least low missing percentage (less than 8%) before starting analysis. Variables with >25% missing data may not be used in modelling but will be summarised and reported.

Missing data patterns will be described, e.g. monotonic, intermittent, etc. Missing mechanism will be also identified as missing complete at random (MCAR), or missing at random (MAR), or missing not at random (MNAR) by using Little's test [4] and graphical inspection [5].

Sensitivity analysis will be performed based on complete case analysis and imputation data analysis. The latter will work on the imputed data using simple imputation or multiple imputation strategies depending on the identified missing mechanism. We will assess how much results change between the results of complete data and the ones using imputation data analysis with different imputation strategies.

6.. Summary of Changes to the Protocol

Additional or supplementary analyses not envisaged in this SAP or in the original protocol may be possible. This SAP will be updated and version-tracked to incorporate any new and potentially useful analysis.

Reference

- [1] Kirkwood BR, Sterne J (2003) Essential Medical Statistics. Blackwell publishing.

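### Section 4 draws its candidate predictors from all of 3.1 to 3.3 without a timing rule, so ECMO duration, repeat ECMO and change of configuration, all determined after ECMO starts, could enter the mortality and length-of-stay models

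*SAP*

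**What the plan says.** The third aim of the SAP is to find factors that predict length of stay, complications and survival. Section 4 defines the regression pool by section number: "It would be useful to perform a regression analysis on the variables listed in 3.1 to 3.3 above". Mortality is to be modelled by logistic regression, and length of stay by Poisson or negative binomial regression.

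Section 3.3, which is inside that pool, lists "Duration of ECMO therapy", repeat ECMO and "Change of configuration during ECMO". Section 3.4 lists "duration of ECMO therapy" again, this time as a secondary outcome. The appendix places it with the features of ECMO treatment. Section 1 restricts the analysis to the first run when a patient has several in one admission.

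Section 4 reduces the pool in several ways. First, "clinical knowledge will decide which variables are important as potential predictors of outcomes". Univariate associations with the primary outcome are then examined. Among highly correlated predictors, one option is to keep "the predictor most strongly associated with the response". Models are compared by likelihood ratio test at p < 0.05, or by AIC if they are not nested. Section 5 adds that variables with more than 25% missing data may be left out. None of these rules refers to when a variable becomes known, and no landmark or time-dependent analysis is planned.

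**The concern.** A predictor of survival or length of stay should be known at the point from which the prediction runs, here the start of ECMO. Three candidates are not.

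- **Repeat ECMO.** Only a patient who leaves the first run alive can have a second. Because only the first run is analysed, a second run in the same admission is a future event relative to it. Used as a fixed covariate for death, it carries immortal-time bias.
- **Change of configuration.** The longer a patient stays on circuit, the more opportunity there is for a change, and death ends that opportunity. This is the same kind of bias, but its direction depends on whether runs ending in death are shorter or longer than the others.
- **ECMO duration.** Against mortality it is a post-baseline variable partly determined by the outcome. Against ICU length of stay it is a component of the outcome, so adjusting for it removes any effect of a baseline factor that acts through time on ECMO.

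At stake is the third aim: the fitted models could report artefacts as independent factors and understate genuine pre-ECMO predictors.

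**Working it through.** The SAP states no figure on this point, so there is none to reproduce. It also gives no rates for deaths, weaning, repeat runs or configuration changes. Every input below is therefore an assumption, and none of the three variables is given a true effect on death.

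**Repeat ECMO and death.** Let p be the share of weaned patients who have a repeat run, and f the share of deaths that occur after weaning. All survivors are weaned, so P(repeat | survived) = p and P(repeat | died) = pf. Hence

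OR = [pf/(1 − pf)] / [p/(1 − p)] = f(1 − p)/(1 − pf).

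For p = 8% and f = 16%: 0.16 × 0.92 / (1 − 0.0128) = 0.1472/0.9872 = 0.15. The last two columns give the share of simulated cohorts in which a univariate likelihood ratio test at p < 0.05 selects this null variable (1,000 patients, 25% mortality, 40,000 simulated 2×2 tables per setting).

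| f | OR, p = 8% | Selected, p = 8% | Selected, p = 3% |
|---|---|---|---|
| 16% | 0.15 | >99% | 82% |
| 27% | 0.25 | 97% | 62% |
| 53% | 0.51 | 58% | 26% |
| 70% | 0.68 | 25% | 13% |
| 80% | 0.79 | 14% | 8% |

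The nominal rate is 5%. Varying p from 3% to 15% moves the OR little: 0.16 to 0.14 at f = 16%, and 0.52 to 0.49 at f = 53%. Under this null the OR reaches 1 only when f = 100%. The cohort of 1,000 is itself an assumption. The 1,317 tracker patients in section 1 are an upper bound, because only those with ELSO records are analysed.

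**Change of configuration and death.** Assume a constant rate λ = 0.02 per day on circuit and gamma-distributed run times with mean m and shape k, so that P(change) = 1 − (1 + λm/k)^(−k). For k = 1 the odds are λm, and the OR equals the ratio of mean run time in deaths to that in survivors. With a survivor mean of 10 days and k = 1, 2 or 4, the OR is 0.74–0.75 at a ratio of 0.75, 1.00 at a ratio of 1, and 1.25–1.27 at a ratio of 1.25.

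**ECMO duration and death.** With the same three ratios, a survivor mean of 10 days, 25% mortality and gamma shapes of 1 to 2, the logistic slope on 400,000 simulated patients gives an OR per day of 0.93–0.97, 1.00 and 1.02–1.04.

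**ECMO duration and length of stay.** Write stay = ECMO time + independent post-ECMO time. A baseline factor that lengthens ECMO by 30% has a true stay ratio of 1 + 0.30 × (ECMO share of stay): 1.12, 1.18 and 1.24 for shares of 40%, 60% and 80%. A negative binomial model that also includes log ECMO duration (60 cohorts of 1,000 per share, gamma shape 1.5) gives about 1.02 in all three cases.

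**Second set of assumptions.** With 1,317 patients, 20–40% mortality, 80% of deaths on ECMO, runs ending in death 20% shorter, 5% repeat runs among those weaned and a mean post-ECMO stay of 8 days, the median ORs were 0.19–0.21 for repeat ECMO and 0.83–0.85 for change of configuration. ECMO duration alone explained 62–63% of the variance in stay.

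**The case against.** Section 4 describes a candidate pool, not a fixed model, and clinical knowledge is the first filter. A competent analyst may drop all three variables, and the listing of ECMO duration as an outcome is a cue to do so. This stands: the harm is conditional. But discretion is not a pre-specified rule, and section 4 brings in the whole of 3.3 by number. Section 3.5 does keep complications out of regression, yet no such exclusion covers these three.

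The data-driven rules are also weaker support than they first appear. Univariate screening has no retention threshold and covers only the primary outcome. The strongest-association rule is an optional way of handling collinearity. AIC applies only to non-nested models. The likelihood ratio test is the one rule that clearly favours keeping such variables, and the selection rates above are univariate whereas the plan selects within multiple regression. These limits are fair, so the rates are illustrations rather than forecasts.

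The size is uncertain too. If most deaths follow weaning, the repeat-ECMO bias is small. If a repeat run truly doubled the risk among weaned patients (p = 8%, 25% mortality), the crude OR would be 0.29, 0.52 or 1.17 at f = 16%, 27% or 53%. For configuration change, and for ECMO duration against mortality, the bias can vanish or reverse. None of this makes the coefficients interpretable: a harmful marker appearing protective is the same fault.

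**Conclusion.** The concern holds. The SAP's stated pool includes three variables determined after ECMO initiation, one of them also an outcome, and nothing in sections 4 or 5 excludes them on timing or handles them as time-dependent.

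The firmest parts are repeat ECMO against mortality, where the bias is downward under the null unless every death follows weaning, and ECMO duration against length of stay, where a real effect of 12% to 24% acting through ECMO time shrinks to about 2%. For configuration change, and for ECMO duration against mortality, size and direction cannot be fixed from the document. Confidence is high that the gap exists; whether it does harm depends on which variables the analysts retain.

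This should be fixed, but it does not touch the primary descriptive result (the percentage discharged alive) or the predefined subgroup variables.

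**What to change.** Replace the definition of the pool in section 4 with wording such as: Candidate predictors are the variables in 3.1 and 3.2 and, from 3.3, only those fixed at ECMO initiation, namely centre, initial modality and, if it is determined at cannulation, transport on ECMO.

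State that ECMO duration is analysed only as an outcome. Report repeat ECMO and change of configuration descriptively or, if event dates are available, by a landmark or time-dependent analysis.

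The cost is a wording change with no new data. Someone must check whether transport on ECMO is determined at cannulation. The models would no longer give coefficients for events during or after the run.

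### The length-of-stay regression has no rule for stays that end in death, so its ratios describe total ICU days and, taken alone, do not separate predictors of stay from predictors of survival

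*SAP*

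**What the plan says.** The third aim is "To identify factors predictive of duration of stay, complications (to be specified) and survival". Section 3.4 defines the primary outcome: "The primary outcome of interest is the % of patients discharged alive from the ECMO ICU". It lists "ICU length of stay" among the secondary outcomes, without restricting it to survivors.

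Section 4 seeks "factors independently associated with the primary outcome (mortality) and the secondary outcome (length of stay, complication". It gives mortality a logistic model and says that "if the outcome is length of stay, Poisson regression or negative binomial regression will be used".

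Three further statements bear on who enters the stay model and how:

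- Section 1 sets the analysed population: "All patients with corresponding ELSO records will be entered into formal analysis".
- Section 4 sets the predictors: "It would be useful to perform a regression analysis on the variables listed in 3.1 to 3.3 above". Vital status at discharge belongs to Section 3.4, outside that list.
- Section 3 contains the only split by survival, and it is descriptive: "A table will be prepared with descriptive variables between survivors and non-survivors".

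Section 5 deals with missing values and does not mention death as ending a stay.

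**The concern.** A stay in the ECMO ICU ends in live discharge or in death. A short stay can therefore mean quick recovery or early death. Nothing in the SAP restricts the stay model to survivors, treats death as a competing event, stratifies by vital status or uses a composite outcome. The SAP does not say outright that all stays are pooled, but that is what its text leads to.

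Two misreadings of the results become possible. A factor that only hastens death would carry a stay ratio below 1 and could be listed as a predictor of shorter stay. A factor that slows recovery and also raises mortality could show a ratio near 1 and be listed as unrelated to stay. At stake is the duration-of-stay part of the third aim.

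**Working it through.** **Inputs.** The SAP gives no stay distribution, mortality rate or effect size, so there is no figure of its own to reproduce. Everything below is assumed: time to live discharge T gamma distributed with mean m = 22 days and CV 0.7 (shape k = 1/0.49 = 2.04), a constant death hazard h, and baseline ICU mortality P0 = 22%. There is one binary factor and no other covariates.

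**Formulas.** Mortality is P = 1 − (1 + h·m/k)^(−k). With a constant death hazard, mean stay is P/h. If the factor multiplies only the death hazard, by HR, the pooled stay ratio is (P1/P0)/HR.

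**Case A: the factor acts on death only.** P0 = 0.220 gives h = 0.0120 per day.

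| Death HR | P1 | Pooled stay ratio |
|---|---|---|
| 1.3 | 0.272 | 0.272/0.220/1.3 = 0.95 |
| 2 | 0.375 | 0.375/0.220/2 = 0.85 |
| 3 | 0.488 | 0.488/0.220/3 = 0.74 |

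At HR 2, mean stay is 18.3 days without the factor and 15.6 with it. Over baseline mortality of 15 to 40% and CV of 0.5 to 1.0, the ratio at HR 2 runs from 0.91 to 0.71. If deaths cluster late (Weibull death times of shape 4), it is 0.94. In a large simulation at HR 2, the live-discharge hazard ratio was 1.00 and the death hazard ratio 2.00. A ratio restricted to survivors was still 0.90, because death removes the longer stays.

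**A second model.** With constant hazards d of live discharge and q of death, the ratio is (d + q)/(d + q·HR). For d = 0.04 per day and 25% baseline mortality, q = 0.04 × 0.25/0.75 = 0.0133. At HR 2 the ratio is 0.0533/0.0667 = 0.80. At 15% and 35% baseline mortality it is 0.87 and 0.74.

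**Case B: survivors' stay unchanged, mortality 22% against 37.5%.** If non-survivors stay r times as long as survivors, the pooled ratio is (1 − P1 + P1·r)/(1 − P0 + P0·r). For r = 0.5, 1.0 and 1.25 this gives 0.91, 1.00 and 1.04. The mortality odds ratio is (0.375/0.625)/(0.22/0.78) = 2.1.

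**Case C: the factor doubles the death hazard and stretches time to live discharge by a multiple a.** The pooled ratio equals 1 when P1 = 2 × 0.22 = 0.44, which needs a = 1.27. The mortality odds ratio is (0.44/0.56)/(0.22/0.78) = 2.8.

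**What tells B from C.** Simulated values, with r = 1 in B and HR 2 in C:

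| | Pooled ratio | Mortality odds ratio (by arithmetic) | Live-discharge HR | Survivors-only ratio |
|---|---|---|---|---|
| B | 1.00 | 2.1 | 0.80 | 1.00 |
| C | 1.00 | 2.8 | 0.70 | 1.08 |

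Both show no pooled effect and raised mortality, so the pooled ratio and the mortality model together do not tell them apart. The live-discharge hazard ratio does so only in part, and the contrast among survivors is also needed.

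**The case against.** The strongest reply is that total ICU days is a natural quantity for a cohort study of a commissioned service, and that a count model on an integer outcome estimates it correctly. That stands. The difference of 18.3 against 15.6 days in Case A is a true difference in ICU days. A reader might infer that the count model is invalid or that 0.85 is a bias. The SAP does not support this, because it never names time to live discharge as its target. What remains is that it does not name total days either, and it sets stay beside survival as a separate target.

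A reader might also infer that Section 4, in asking for independent associations, requires stay effects to be free of survival effects. It does not. In a passage on confounders and collinearity, the phrase means adjusted for other covariates.

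Third, the live-discharge hazard ratio moves with mortality too. In Case B with equal stays, the count model gives 1.00 and the live-discharge hazard ratio is 0.80, although survivors' stay is unchanged. This also stands. It is why the cause-specific models should be added to the count model and not put in its place.

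Fourth, the figures are for one factor. Section 3.3 supplies duration of ECMO therapy as a candidate predictor. In an illustration with assumed ECMO and post-ECMO phases of 11 days each, adjusting for it moved Case A from 0.83–0.87 to about 0.89 and Case C from 0.96–1.01 to about 0.93. The exact cancellation in Case C is therefore not robust, although the mixing with death remains.

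Finally, the mortality model and the survivor table already give partial information, and the table may well include stay. Neither changes what the stay coefficients measure. The protocol, which is not shown, may define the outcome more closely, but it is this SAP that chooses the stay model.

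**Conclusion.** The point holds in a limited form. The SAP fixes a count model for length of stay and has no rule for death. As written, its ratios describe total ICU days. They are valid for that, but read alone they mix earlier death with faster live discharge.

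The mechanism needs no particular input, but its size does. The pooled ratio of 0.85 for a doubled death hazard rests on the assumed stay distribution, the assumed mortality and a single factor, and it is close to 1 for weak effects (0.95 at HR 1.3) or late deaths (0.94). Case C shows that masking is possible, not that it is likely.

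The issue is minor to moderate. It is worth fixing because stay is a named target of the third aim, but it concerns a secondary outcome and leaves the primary outcome untouched.

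**What to change.** Amend the length-of-stay clause in Section 4 along these lines:

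- *Negative binomial regression of ICU days in all patients is reported as an analysis of total ICU days (resource use).*
- *Cause-specific hazard models are fitted for discharge alive from the ECMO ICU and for death in the ECMO ICU, and are reported together.*
- *Length of stay is reported by vital status, including each main factor's stay contrast among survivors as a descriptive result.*
- *No single coefficient, including the live-discharge hazard ratio, is read as an effect on stay without the death model beside it.*

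The variables needed, ICU length of stay and discharge alive, are already in the appendix. The second must be status at discharge from the ECMO ICU, to match Section 3.4.

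The cost is SAP wording, two further models from a standard survival routine, a proportional-hazards check, and ratios that are less intuitive than days.
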